**Data Storage/Record Retention**

Data	Pre and post measures of	Intervention	Control	Monitor only	Program Evaluation	Source
Length of Stay (LOS)	LOS or average LOS(s) at hospitalisation	✓	✓	✓	✗	Data Ware-House

Hospital Admissions	Number of hospitalisations in past 12 months	✓	✓	✓	✗	Data Ware-House	F v f c E f
ED Presentations	Number of ED presentations in past 12 months	✓	✓	✓	✗	Data Ware-House	F v f c E f
Quality of Life	Specific validated questionnaire	✓	✓	✗	✗		F v f c E f
Health Literacy \ Self management	Specific validated questionnaire	✓	✓	✗	✗		F v f c E f
Mortality		✓	✓	✓	✗	Hospital Data	F v f c E f
PRaDA	Predictive value of the patients (intervention vs control vs followed)	✓	✓	✓	✗	PRaDA	F v f c E f
Interviews	NA	✗	✗	✗	✓	Word files/PDF password	

						protected
--	--	--	--	--	--	-----------

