#### **Centre for Pattern Recognition and Data Analytics (PRaDA)**

Barwon Health has recently formed a partnership with Deakin University's, Centre for Pattern Recognition and Data Analytics (PRaDA). The Centre is currently analysing Barwon Health's hospital admission data and has ethical approval to do so. This type of analysis provides an innovative way to review, and identify, groups of consumers admitted to the acute hospital, as well as the likelihood of future admissions. A number of techniques utilised including detailed word association analysis. This enables Deakin University and Barwon Health professionals to understand the 'drivers' of anticipated hospital admissions. The availability of this data, and its associated analysis, will provide enhanced rigour in selecting a population that the Barwon Health Personalised Health Care model can test as a pre-emptive hospital avoidance model.

Using computer modelling the data analysis aims to expose latent patterns in health data and medical records, and assign individuals to these patterns. The method uses characteristics of individuals such as diagnosis, co morbidities, age, gender, admission & length-of-stay history, diagnosis procedures (rarity is also emphasised) past HbA1c measures, past operations and past medications to predict the likelihood of no admission to an acute hospital in the next 12 months. Based on the data analysis, a resultant likelihood of no admission between 0 and 1 can be assigned to a patient. This method has been performed on 2008-2010 Barwon health data with developers being blinded to 2011 data, which has then been used for validation. A paper describing this methodology and its accuracy is currently under review for publication at a peer reviewed journal. Figure 1 below shows the results of this analysis

Figure 1 Probability that a group of patients will NOT be readmitted in the next 12 months

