## **2. AIMS/OBJECTIVES/HYPOTHESES**

### **Aims/Objectives**

To evaluate the effects of the personalised health care program which includes care plans, escalation process and tele-health on:

- ED admissions
- Acute Admissions
- LOS on acute admission
- Self-reported GP appointments
- To understand the effects of a model of care on health literacy and self-management
- To assess appropriate outcome measures for a fully powered randomised controlled trial
- To assess the variability of outcome measures to aid in sample size calculation for a fully powered randomised controlled trial
- Recruitment and retention rates
- Compliance with self-reporting
- Qualitative Interview
- Survey

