### **Selection Criteria**

#### *Inclusion criteria*

- Diagnoses of COPD or Diabetes (Type I and Type II)
- PRaDA “likelihood of admission in the next 12 months” value of 0.5-0.8
- Lives in own home

- Over 18 years of age
- Ability \ dexterity to enter and submit own data via a computer or similar device.
- English speaking or carer who is English speaking
- Willingness and ability to take own vital signs and biometric readings via appropriate selected device (e.g) a glucose meter or live with a carer who can.

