**Allocation method**

Individuals will be allocated by a stratified minimisation randomisation algorithm. Stratification variables will be the individual’s primary diagnosis (COPD/diabetes), and the baseline PRaDA risk of readmission in the following 12 months. The risk strata will consist of four evenly spaced risk sets (0.60-0.65, 0.65-0.70, 0.70-0.75, 0.75-0.80). The minimisation algorithm will be implemented within the study’s enrolment database.

Individuals agreeing to involvement in the study, and who are subsequently allocated, will be assigned a (sequential) allocation number; the combination of the screening number and the allocation number (for example, XXXXX-XXX) will give the unique individual study number. A master file containing individual UR, name, date of birth and study number will be stored separate to other study documents. This allocation and randomisation process will be guided and performed by [name] (Barwon Health Statistician\ Research Fellow)

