### **Methods**

Due to the pilot nature of the study, analysis of study data will not follow a hypothesis testing framework. Confidence intervals for efficacy outcomes will be calculated within each group at the 95% confidence level, however no formal significance tests will be made. Hospital admissions will be treated as a binary variable, ED presentations as counts, and LoS as ordinal. Total LoS (summed over all admissions) will be presented.

Allowances for stratification of the sample will be made via the Cochran–Mantel–Haenszel (CMH) test for unadjusted analyses, and adjustment for covariates will further be investigated via logistic regression for binary variables; adjustment for covariates will use Poisson regression for count variables. Analysis of the readmission rates will further be summarised under a time-to-event framework.

Baseline measures will be summarised by group, as will any differences post-intervention. Trial procedures (such as recruitment and retention rates, compliance and monitoring loads) will be monitored and summarised by confidence intervals where appropriate.

Following verbatim data transcription of each interview, a constant comparative thematic analysis method will be used. Two researchers will analysis the data independently and confer to confirm the thematic structure of the data.

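### Length of stay is worded in three non-equivalent ways, and the per-stay or average version gives no value to patients without an admission

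*Protocol*

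**What the plan says.** LOS appears in four places in the Protocol.

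- **Synopsis (Criteria for Evaluation) and section 2 (Aims/Objectives):** the item is "LOS on acute admission".
- **Section 9, Data Storage/Record Retention:** the LOS row, under a column for pre and post measures and ticked for both randomised arms, reads "LOS or average LOS(s) at hospitalisation".
- **Section 10, Statistical analyses, Methods:** "Hospital admissions will be treated as a binary variable, ED presentations as counts, and LoS as ordinal". The next sentence adds: "Total LoS (summed over all admissions) will be presented".

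None of these says which version is the analysed outcome, or what value a patient with no admission receives.

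How many patients would have no admission depends on the PRaDA score, which the Protocol describes inconsistently. The inclusion criterion is "PRaDA “likelihood of admission in the next 12 months” value of 0.5-0.8". The Allocation method states: "The risk strata will consist of four evenly spaced risk sets (0.60-0.65, 0.65-0.70, 0.70-0.75, 0.75-0.80"). The background on PRaDA says that "a resultant likelihood of no admission between 0 and 1 can be assigned to a patient", and Participant Identification in section 4 also refers to a likelihood of no admission.

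**The concern.** A single stay, a patient's average stay and a patient's total days are different outcomes. The total is defined for everyone randomised. The other two exist only for patients who were admitted, and reducing hospital use is what the program sets out to do. Comparing stay among the admitted therefore compares two groups formed after randomisation, possibly by the intervention itself.

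No p-value is at stake, because the pilot plans no hypothesis tests. What is at stake is the pilot's stated purpose of identifying suitable outcome measures and their variability for a fully powered trial. The mean, the variance and the evaluable fraction of LOS all depend on which version is meant. Leaving the choice open until the data are seen also leaves room for selective reporting.

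**Working it through.** The Protocol gives no LOS target, effect size or power, and the sample size is set by funding, so there is no stated figure to reproduce.

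**1. Are the versions interchangeable?** Take two hypothetical patients. A has one 6-day stay: total 6, average 6. B has stays of 6, 2 and 2 days: total 10, average 10/3 = 3.3. The total ranks B higher and the average ranks A higher, so an ordinal analysis depends on the choice. In the same data table, admissions and ED presentations are counts over the past 12 months, which give every patient a value. The LOS row is tied to a hospitalisation and does not.

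**2. How many patients have no per-stay or average value?** Inputs: 200 per arm (Synopsis) and the score ranges above. Formula: share unscored = 1 − P(admission). This assumes that the score is calibrated.

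| Reading of the score | P(admission) | Unscored | Unscored per arm of 200 |
|---|---|---|---|
| Inclusion criterion, likelihood of admission | 0.5-0.8 | 20-50% | 40-100 |
| Allocation strata | 0.60-0.80 | 20-40% | 40-80 |
| 0.5-0.8 read as likelihood of no admission | 0.2-0.5 | 50-80% | 100-160 |

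With total days and 0 for no admission, all 200 per arm are scored. For a pre-to-post change, a per-stay or average value would require an admission in both years, so the loss would be at least as large.

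**3. Can the average move against the total?** This is an illustration; none of its inputs comes from the Protocol except that 65% lies within the entry range. Assume that:

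- control admissions are Poisson with rate λ per patient-year;
- half last 2 days and half 8 days;
- the program prevents half of the 2-day admissions and none of the others.

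Formulas:

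- λ = −ln(1 − P(admission)); at 65%, λ = −ln(0.35) = 1.050.
- Total days per randomised patient: control (λ/2)×2 + (λ/2)×8 = 5λ; intervention (λ/4)×2 + (λ/2)×8 = 4.5λ.
- Mean of patients' average stays among the admitted (under this model equal to the mean stay per admission): control 5λ/λ = 5.0; intervention 4.5λ/0.75λ = 6.0.
- Share with no admission: control exp(−λ); intervention exp(−0.75λ).

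| Control P(admission) | λ | Total days, control to intervention | Average stay among admitted | No admission |
|---|---|---|---|---|
| 0.50 | 0.693 | 3.47 to 3.12 | 5.0 to 6.0 | 50% to 59% |
| 0.65 | 1.050 | 5.25 to 4.72 | 5.0 to 6.0 | 35% to 45.5% |
| 0.80 | 1.609 | 8.05 to 7.24 | 5.0 to 6.0 | 20% to 30% |

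Total days fall by 10% (4.5/5) while the average rises by 20% (6/5). At 65%, the average would leave out 0.35×200 = 70 controls and 0.455×200 = 91 intervention patients. A simulation of 400,000 patients per arm agreed to within rounding.

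**4. Does this hold without the selective effect?** Remove the same quarter of admissions regardless of length. The total becomes 0.75×5λ = 3.75λ (−25%) and the average stays at 5.0. The sign reversal disappears. The unequal loss of patients between arms does not, since exp(−0.75λ) still applies.

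**The case against.** The best defence is that the plan already names the total. The Methods are the only place that says how outcomes are analysed, and the sentence on total LoS directly follows the one on ordinal treatment. Zero for no admission follows naturally, and spelling it out is commonly left to a statistical analysis plan. The item in the objectives is a short label, and its word 'acute' may only say which stays count. The section 9 table lists data and sources rather than endpoints, and its text is damaged in extraction, so a qualifying entry may be lost. A pilot that is assessing outcome measures may also reasonably report more than one LOS summary.

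Much of this stands. It makes the total the best-supported reading and the point moderate. It does not remove the conflict. The table names a per-stay or average value, with the choice left open, as the pre and post measure in both randomised arms. An analysis plan that chose either version would depart from one part of the Protocol.

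Three stronger readings are tempting and are not supported.

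- A reader might infer that the program would be reported as harmful on LOS. The Methods commit to presenting the total, plan within-group intervals and no formal tests, and nothing in the Protocol says that short admissions would be prevented first.
- A reader might take the illustration as calibrated to the 5-6 day stays quoted in section 1. Those are medians, for COPD only and by age group. The illustration uses assumed stays with a mean of 5, and the trial also enrols patients with diabetes.
- A reader might treat 20-50% without an admission as the trial's expectation. It is one of three readings of a score that the Protocol describes in opposite directions.

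**Conclusion.** The point holds at moderate weight. The Protocol gives LOS measures that are not the same outcome, and the one recorded in section 9 has no value for patients without an admission. The loss is substantial on every reading of the score (at least 20%, or 40 of 200 per arm, if the score is calibrated). A comparison of arms on that version also conditions on something that the intervention is meant to change. That much needs no assumption about which stays are prevented.

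Movement in opposite directions (−10% in total days with +20% in average stay) shows only what can happen if mainly short admissions are avoided. It is not a prediction. The practical consequence is a comparison open to bias and, if the average were carried forward, a mean and variance for the wrong outcome in planning the later trial.

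**What to change.** Use one definition in the Synopsis, section 2, the section 9 data table and the section 10 Methods: total acute inpatient days over the 12 months after allocation, per randomised patient, scored 0 when there is no acute admission. Apply the same definition to the 12 months before allocation for the pre measure. Keep the acute qualifier, so that non-acute stays do not enter through the rewording. State in the Methods that this total is the LoS analysed as ordinal.

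Average stay per admission can remain as a descriptive figure among admitted patients, labelled as not a randomised comparison.

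The cost is wording in four places. The data warehouse named in section 9 is already the source, so no new data are needed. The small downside is a skewed outcome with many zeros, which the planned ordinal treatment accommodates.

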**Expected Duration of Study/Start Times**

Participants will receive the intervention over a 12 month period. Recruitment is anticipated to begin in late September 2013. There will be a 6 month period of recruitment to achieve the maximum of 400 patients for the intervention and control arms. Full recruitment (400) is anticipated to be achieved by March 2014.

**10. OUTCOMES AND SIGNIFICANCE**

**Statistical Analyses**

**Sample Size (n=400)**

In similar models of care operating, one nurse monitors approximately 100 patients. In line with this, our proposed service model aims to provide proof of concept for this approach. The funding provided by the Department of health to operate the pilot model of care, is specified for 200 patients over a period of 18 months. Therefore the “*Intervention Group*” sample size will be a maximum of 200. The “*Control Group*” will also be 200 in order to monitor comparative changes.

**Participant numbers**

Individuals identified as potential participants will be allocated a screening number in sequential order. This number will be allocated in a sequential fashion as responses to the initial trial invitation are received by the Returning Officer. Allocation of participants to either the intervention or control arm will be made at the time of consent (as indicated by the signing of the PICF).

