## **6. TREATMENT OF SUBJECTS**

At the patient's first appointment they will have the opportunity to discuss the information provided in the Participant Information and Consent Form (PICF) with the program staff. If the participant understands the information provided, is satisfied with the responses to any questions they have, and agree to participate they will be asked to provide informed consent by signing the PICF (please see appendix B for consent form). Patients unwilling to participate in the pilot or sign the consent form will not be enrolled and will not be contacted again.

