### **Baseline Initial assessment and at 12 months - measures and observations**

Diabetes cohort

- Diabetes Type I or II
- HR, Rhythm
- Blood Pressure
- current HbA1c
- Serum Lipids
- Urine micro albumin
- Weight/height (BMI)
- Summary of health status including complications
- Medications including adjustment regime
- Validation/quality control of individual meter documented
- AQoL
- Health Education Impact Questionnaire
- Interview
- Survey

COPD cohort

- Recent lung function test
- HR, Rhythm
- Blood Pressure
- Weight/height (BMI)
- Barwon Health Respiratory Initial Health Assessment Tool
- 6 min walk test
- Mental health screen (K10)
- COPD Assessment Test (CAT)
- Summary of health status including complications

- Medications including adjustment regime
- AQoL
- Health Education Impact Questionnaire
- Interview
- Survey

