## **8. EFFICACY EVALUATIONS**

### **Participant training and confirmation of care plan**

Following identification as per the research protocol, clients will be contacted by the program staff who will introduce the program and, as per the research protocol, enrol the client in one of the two cohorts through a randomisation process as described in the statistical analyses section.

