### **Initial Visit**

Following agreement for enrolment and identification into the intervention group a staff member from the program will again contact the client the details of the persons care plan will be developed in consultation and authorised by the clients usual treating consultant \ GP. Prior to the commencement of the pilot study, all participants will be asked to complete Health Literacy and Self-Management questionnaires as well as at specific intervals over 12 months

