### **Personalised Health Care Remote Patient Monitoring System**

The Remote Patient Monitoring (RPM) system used in this pilot project is a web based platform that can be accessed from any internet connected device. The patient, when accessing the platform, will be directed to their personalised care plan that has a questionnaire designed to educate and guide the client to monitor and support their own health. The peripheral devices that link to the system, enable the monitoring of clinical signs and symptoms such as SaO2, blood pressure and blood glucose measures.

For the health service clinicians accessing the platform, the RPM system identifies in real time which clients have recorded results at that point in time and which have not, it provides an indication of which results are at variance to the result parameters set for each individual, thus enabling a rapid and timely response.

The RPM system generates individualised reporting that allows the clinicians to monitor trends within a client's health care over time, enabling treatment to be appropriately adapted as and if required.

The client is required to log in to the system daily, to answer questions about their health and monitor aspects of their health. If clients do not complete their daily monitoring, the RPM system will alert the health service clinicians to this for follow up. The model is only as effective as the level of participation of the client, therefore for clients that are not willing or able to participate by choice or otherwise will need to be identified early, be removed or request to withdraw from the study.

Clients may choose to use their own web connected device to access the RPM system or alternatively Barwon Health will provide a suitable hardware device. If clients choose to use their own internet connected device, appropriate screening will be performed to ensure the device is suitable for purpose, including the quality of internet connectivity at the client's location. Client's using their own internet connection will be reimbursed at an appropriate rate for the amount of data transferred for the purpose of their RPM according to the data rates identified by the preferred vendor. If required Barwon Health will reimburse Internet costs or pay for new connections. If connectivity is not possible due to a patient's residential location, patient will be excluded from participation

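### Allocation is fixed at the signing of consent, so self-reported baseline measures may be collected after the arm is known, and the connectivity exclusion may fall after allocation on the intervention arm alone

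*Protocol*

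**What the plan says.** **Allocation.** Section 10, Participant numbers: "Allocation of participants to either the intervention or control arm will be made at the time of consent", with consent defined as signature of the consent form. Section 6 places that signature at the first appointment, where patients who "agree to participate they will be asked to provide informed consent by signing the PICF".

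**Baseline.** The next part of section 6 is headed "Baseline Initial assessment and at 12 months - measures and observations". It lists AQoL and the Health Education Impact Questionnaire for both cohorts, and adds the K10, CAT and six-minute walk for COPD. Section 8, Participant training and confirmation of care plan, has programme staff introduce the programme and "enrol the client in one of the two cohorts through a randomisation process as described in the statistical analyses section". The Initial Visit text follows: "Following agreement for enrolment and identification into the intervention group a staff member from the program will again contact the client". The same paragraph then says: "Prior to the commencement of the pilot study, all participants will be asked to complete Health Literacy and Self-Management questionnaires".

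**Connectivity.** Section 8, on the Remote Patient Monitoring System, says: "If connectivity is not possible due to a patient's residential location, patient will be excluded from participation". The inclusion and exclusion lists in the Synopsis and section 4 do not mention connectivity.

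**The concern.** Two features of a sound randomised comparison depend on the order of steps at entry.

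First, baseline values should be recorded before anyone knows the arm. No blinding is described, and nurses employed on the programme enrol and consent the patients. A patient who has just learned that they will, or will not, receive monitoring may rate their health or self-management differently. The Study Plan measures health literacy and self-management at baseline and 12 months to see whether they improve, so a shift in the starting value carries straight into change from baseline. No analysis can recover a baseline unaffected by allocation afterwards.

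Second, eligibility should be settled before allocation. If patients are excluded afterwards for a reason that arises only in one arm, the arms stop being the groups that were randomised. The stated reason is where the patient lives, so the loss need not be random. It would also lower retention in one arm by construction, and retention is a stated objective meant to inform the full trial.

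**Working it through.** The protocol gives no figure to reproduce on this point. The planned 400 is 200 + 200, set by funding, with no standard deviation, effect size or dropout rate. The check is therefore of sequence first, then an illustration on assumed inputs.

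**1. Order of steps in the text**

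| Step | Where | Timing given |
|---|---|---|
| Consent signed | Section 6 | First appointment |
| Allocation | Section 10, Participant numbers | At signature of consent |
| Baseline measures | Section 6 | Listed after consent; not placed before allocation |
| Questionnaires | Section 8, Initial Visit | Before the pilot study commences; start point undefined |
| System set-up | Section 8, Follow-up visit | Second home visit, after allocation |
| Connectivity exclusion | Section 8, Remote Patient Monitoring System | None |

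Measures taken for the research need consent. If allocation coincides with consent, no interval is reserved for a baseline taken without knowledge of the arm. The connectivity rule is absent from eligibility and belongs to a system that only the intervention arm uses. The protocol describes no matching check for controls.

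**2. Connectivity exclusion and admissions (assumed inputs)**

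Let p be the 12-month admission risk, d the share of the intervention arm excluded after allocation, and q the risk of those excluded. With no treatment effect, the risk among the intervention patients who remain is (p − d·q)/(1 − d).

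- p = 0.65: assumed, the midpoint of the 0.5–0.8 PRaDA entry range.
- q = 0.5 or 0.8: assumed, the ends of that range.
- d = 2% to 20%: assumed.

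For d = 5%, q = 0.5: (0.65 − 0.05 × 0.5)/0.95 = 0.625/0.95 = 0.6579, a spurious difference of +0.79 points. For q = 0.8: 0.61/0.95 = 0.6421, or −0.79 points.

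| d | Intervention patients left | Largest shift (points) |
|---|---|---|
| 2% | 196 | ±0.31 |
| 5% | 190 | ±0.79 |
| 10% | 180 | ±1.67 |
| 20% | 160 | ±3.75 |

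If q = p the shift is zero. The 95% half-width for the arm difference at d = 5%, q = 0.5 is 1.96 × √(0.65 × 0.35/200 + 0.6579 × 0.3421/190) = 9.4 points. Over the whole grid it runs from 9.4 to 10.0.

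**3. Retention**

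At d = 2–5%, 4–10 of 200 intervention patients are lost and no controls, so intervention-arm retention is capped at 98–95% from this cause alone.

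**4. Self-reported outcomes (assumed inputs)**

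Suppose knowledge of the arm moves one arm's baseline mean by δ standard deviations and leaves the 12-month value alone. Let ρ be the correlation between baseline and 12 months. With 200 per arm, √(2/200) = 0.10 SD. Then:

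- 12-month values only: bias 0, standard error 0.10 SD.
- Change scores: bias of size δ, standard error 0.10 × √(2(1 − ρ)) SD. At ρ = 0.5 this is 0.10 SD, so δ = 0.1–0.2 gives one to two standard errors.
- Baseline-adjusted: bias of size ρδ. At ρ = 0.5 that is 0.05–0.10 SD.

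Neither δ nor ρ is in the protocol.

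**The case against.** The order is not stated outright, and several passages leave room for a better one. The questionnaire sentence in Initial Visit covers all participants and could be meant as before allocation. Section 10, Allocation method, speaks of people who agree and are then allocated, which allows an interval. Allocation at consent could mean at the same appointment. The Appendix A flow chart, which is not shown, may settle it. These points stand as ambiguity. None of them requires baseline to come first, and the explicit sentence ties allocation to the signature.

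A reader might infer that connectivity failure is discovered at the second home visit and that controls are never checked. The text supports neither. The Follow-up visit paragraph does not mention connectivity, the exclusion sentence has no time point, and the protocol is silent on controls. The exclusion could even be an entry condition, but then it should be in the eligibility lists.

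The number excluded may be very small, because the sponsor will supply hardware, reimburse internet costs and pay for new connections where required. That stands: only locations where connection is impossible remain, and the 2–5% used here has no source in the protocol.

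Admissions, ED presentations and length of stay come from the data warehouse, and PRaDA risk comes from records, so arm knowledge cannot alter their baseline values. That also stands, and confines the baseline problem to self-report and effort-dependent measures, some of them collected in COPD only.

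Finally, the analysis set is commonly left to a statistical analysis plan, and this is an unpowered pilot without formal tests. Both are fair, but the order of entry procedures is a matter of trial conduct that an analysis plan cannot repair.

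**Conclusion.** The point holds as a defect in what the protocol permits. Followed as written, it allows self-reported baseline data to be collected with the arm known, and a connectivity exclusion to fall after allocation on one arm only. It does not show that either must happen.

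For admissions the distortion is probably minor: up to 0.3–0.8 percentage points at an assumed 2–5% exclusion, well inside a half-width of about 9–10 points. A claim that comparability on hospital use is materially broken would go too far.

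The main concern is change from baseline in the self-reported outcomes, together with the retention rate. A reader might put the former at one to two standard errors, but that needs an assumed shift of 0.1–0.2 SD, a change-score analysis and a correlation near 0.5. Its size cannot be derived from the protocol. The point is worth acting on because the remedy is cheap and the loss of a clean baseline cannot be undone.

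**What to change.** Reword Participant numbers in section 10 so that allocation is the last entry step, in this order:

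1. consent;
2. an internet and device check for every participant;
3. completion of the baseline questionnaires and measures;
4. the minimisation call.

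Add connectivity to the eligibility criteria in the Synopsis and section 4. Reconcile the section 8 paragraphs on participant training, Initial Visit and the monitoring system with this order, and confirm that the Appendix A flow chart agrees. State that a patient whose connectivity fails after allocation stays in the analysis in the allocated arm.

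With the check done before allocation, the spurious difference from connectivity exclusion is zero for any exclusion rate and any risk among those excluded, and baseline is answered without knowledge of the arm.

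The cost is a reordering of planned steps and a short connectivity check for people who become controls.
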